9.2 Anticipated and Unanticipated Adverse Device Effects

PrismRA arm:

PrismRA is not expected to result in either anticipated or unanticipated adverse device effects (UADE) as it involves the analysis of ex-vivo blood samples from the participating patients.

This study does include a potential source of harm to the patient as a result of the venipuncture procedure, unrelated to the study device:

- Faintness, inflammation of the vein, bruising, temporary discomfort, and bleeding at the site of puncture may occur.
- Infection may also occur, though rare.

External control arm:

Data arise from routine clinical practice and do not involve the use of the PrismRA test. Thus, no study-relevant adverse device effect exists.

10 Statistical Considerations

Data collected throughout this study will be analyzed by Sponsor or its designee.

10.1 Sample size

The study is powered to detect a difference of 10% in the proportion of patients with improvement in CDAI from baseline to Week 24 by at least MID as defined in Section 7.1 between the PrismRA arm and the external control arm. Results are shown in Table 3. It is estimated that the attrition rate at Week 24 (defined as the proportion of patients with missing CDAI scores at Week 24 for any reason) can be up to 45% in the PrismRA arm and up to 50% in the external control arm. The sample sizes below have been inflated accordingly to account for the patient attrition mentioned above.

With a sample size of 600 in the trial arm and 1,500 in the external control arm, the study has 88% power to establish the superiority of the PrismRA intervention as compared to the standard of care by detecting a difference of 10% between the two study arms based on Fisher's exact test of independent proportions assuming the proportion of patients with improvement in CDAI by MID are 40% and 30% in the PrismRA arm and the external control arm, respectively.

Table 3. Study power for comparing proportion of patients with improvement in CDAI from baseline by at least MID between the two study arms

Sample size in the trial arm before attrition	Sample in the external control arm before attrition	Proportion of patients in the PrismRA arm with MID improvement in CDAI	Proportion of patients in the external control arm with MID improvement in CDAI	Study power	Alpha (two-sided)
600	1,000	0.45	0.35	80%	0.05
600	1,000	0.40	0.30	82%	0.05
600	1,000	0.35	0.25	85%	0.05
600	1,500	0.45	0.35	86%	0.05
600	1,500	0.40	0.30	88%	0.05
600	1,500	0.35	0.25	90%	0.05
600	2,000	0.45	0.35	88%	0.05

600	2,000	0.40	0.30	90%	0.05
600	2,000	0.35	0.25	92%	0.05

The sample size calculation was performed with SAS (version 9.4, Cary, NC).

10.2 Planned Interim Analysis of the PrismRA Arm

Data will be assessed by the Scipher Medicine team in one interim analysis when 50% of enrollees in the PrismRA arm have completed the treatment initiation visit. Refer to the study's SAP for additional details.

10.3 Baseline Analysis of the External Control Arm

The OM1 team will identify an eligible pool of patients for an external control arm in the OM1's PremiOM RA dataset.

The baseline study data from the PrismRA arm will be provided by the Scipher Medicine team in a format ready for analysis (fully quality controlled), with a corresponding dataset specification document to help the OM1 team understand the data.

From the pool of the study-eligible RA patients in the OM1 PremiOM RA dataset, the external control patients will be selected based on propensity scores. Analytic approaches which adjust for differences in patient baseline characteristics will be used. These approaches include but are not limited to propensity score weighting, matching and covariate adjustment in a multivariable regression model.

Baseline covariates including the following will be considered (defined in a 6-month window prior to the index date unless otherwise specified elsewhere).

Domain	Variables
Patient Characteristics	
 • Age (calculated from birth year) • Sex • Race/Ethnicity • Geography • Body mass index
Lifestyle	
 • Smoking (current, former, or never smoker)
Comorbidities (based on at least two diagnostic codes at least 30 days apart in the external control arm; based on an additional questionnaire in the PrismRA arm.)	
 • Lung disease • Myocardial infarction • Other cardiovascular • Stroke • Hypertension • Fractures spine, hip, or leg • Depression • Diabetes mellitus

	
 • Ulcer or stomach problem • Fibromyalgia 
The Rheumatic Disease Comorbidity Index (RDCI) will be derived.

RA Related	
 • Duration of RA (Defined as the number of days between the date of the first RA diagnosis code and the index date for the external control arm) • Seropositivity (rheumatoid factor or anti-citrullinated peptide antibody) • CDAI at baseline • Previous use of TNFi (yes, no)
Concurrent RA Medications	
 • Methotrexate • Folic acid • Non-methotrexate major csDMARDs (Sulfasalazine, Leflunomide, Hydroxychloroquine) • Glucocorticoids (with prednisone equivalent dose)

The choice of TNFi vs. non-TNFi b/tsDMARDs as the study treatment will be excluded from the list of potential propensity score variables, as this variable is temporally subsequent to the study's exposure variable (use or non-use of PrismRA in the trial arm and external control arm, respectively) and is considered a mediator of the potential benefit of PrismRA.

The baseline characteristics of patients will be compared across the PrismRA arm and the external control arm both before and after the propensity score modelling procedure in a table. In general, each continuous variable will be reported as mean, standard deviation (SD) or median, interquartile range (IQR), and range where appropriate. Each categorical variable will be summarized as a number and proportion. The baseline characteristics after propensity score modeling will be examined for improved covariate balance via the absolute standardized mean metric for each covariate.

Complete details regarding the planned analyses are available in the study SAP.

10.4 Planned Outcome Analysis

The previously stated outcome measures will be compared across the PrismRA arm and the external control arm after propensity score modelling. For all outcome measures, point estimates as well as two-sided 95% confidence intervals (CIs) will be provided. Hypothesis testing will be

two-sided with an alpha level of 5%. For proportion outcome measures, Pearson's χ^2 test will be utilized. For continuous outcome measures, unpaired t-test will be used.

Refer to the study's SAP for additional details.

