5.3 Data Summarization and Analysis

Summary statistics for continuous variables to be reported will include mean, median, standard deviation (SD), 25th and 75th percentile. Categorical variables will be reported using counts and proportions. Hypothesis testing will be two-sided with an alpha level of 5%. For all outcome measures, point estimates as well as two-sided 95% confidence intervals (CIs) will be provided. P-values will be reported where appropriate to four decimal points unless all p-values in a table are greater than 0.01 in which case p-values will be reported to three decimal points in that table as the fourth decimal point is not needed. Details of the specific analytic methods are described below (Section 6).

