Propensity score matching. Patients in the external control arm will be PS matched with participants in the PrismRA trial arm within strata.[22] Individuals will be matched on the logit-transformed PS using an optimal nearest-neighbor without replacement method within calipers.[23] Optimal matching will be used to minimize the total absolute difference in the logit PS across all matches. [24] Caliper widths will be determined based on the SD of the logit of PS (e.g., $0.2 \times \text{SD}$). [25 26] In order to avoid excluding unmatched PrismRA patients an upper limit

of the caliper width (e.g. $0.3 \times \text{SD}$ of the logit PS) will be specified before expanding the historical control period (as described in Section 5.2). Each PrismRA arm subject will be matched with between one and three external control arm subjects using a variable matching ratio, and the targeted total number of matched external control arm subjects will be approximately twice the size of PrismRA arm. [27] Matched external control arm patients will be further weighted based on the following principle: if a PrismRA arm patient is matched to x controls, then these matched controls will be assigned $w = \frac{N_c}{xN_t}$, where N_t is the total number of matched PrismRA patients and N_c is the total number of matched control patients. Propensity score matching is used to estimate the average treatment effect for the treated (ATT), which provides an estimate of the treatment effect among patients who ultimately received treatment. [16]

Imputation of missing outcome data. All eligible patients meeting inclusion and exclusion criteria and initiating the study treatment will be included in MI models for handling missing outcome data as specified in Section 5.4.

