6.3.1 Main Analysis

Main analyses will proceed according to the following order of procedures:

- 1) Perform single imputation for all missing pre-treatment covariates.
- 2) Estimate the probability of treatment with PrismRA for matching. Only pre-treatment covariates will be included as predictors of treatment (e.g., blinded to outcomes).
- 3) Perform stratified PS matching and describe patient characteristics of this single matched cohort. Matched external control arm should be weighted following the principle in Section 6.3 before describing patient characteristics.
- 4) Impute missing outcome data using MI as described in Section 5.4.
- 5) Within each imputed dataset, fit treatment effect outcome model with arm assignment as the independent variable with covariates adjustment.
- 6) Pool treatment effect estimates using Rubin's rule.

Steps 1-4 will be performed once at the start of analyses for each analysis population. Steps 5 and 6 will be repeated for each study endpoint and for the Treatment Policy Strategy and Composite Strategy.

Outcome regression models may also include direct adjustment for important patient covariates (e.g. age, sex, race/ethnicity, RDCI, baseline scores). In general, these methods improve confounding control in cases of imperfect matching and stratification. [30] The proportion of patients within each study arm with moderate or high disease activity at baseline who achieve an MID in CDAI of ≥ 6 (baseline moderate) or ≥ 12 (baseline high) at 24 weeks after study treatment initiation will be reported. Odds ratio and 95% CI will be estimated using weighted logistic regression.

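### The test that decides the primary comparison is not reconciled: Protocol 10.4 names Pearson's chi-square and an unpaired t-test, the power sections name Fisher's exact test, and the SAP fits weighted regression to variable-ratio matched data

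*Protocol*

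**What the plan says.** Three methods are attached to one primary comparison.

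- **Power (Protocol 10.1, repeated in SAP 5.1).** Superiority is powered on Fisher's "exact test of independent proportions assuming the proportion of patients with improvement in CDAI by MID are 40% and 30" per cent.
- **Outcome analysis (Protocol 10.4).** Outcomes "will be compared across the PrismRA arm and the external control arm after propensity score modelling". Testing is "two-sided with an alpha level of 5" per cent. For proportions Pearson's chi-square "test will be utilized. For continuous outcome measures, unpaired t-test will be used". The section closes with "Refer to the study's SAP for additional details".
- **SAP 6.3, 6.3.1 and 6.4.1.** "Each PrismRA arm subject will be matched with between one and three external control arm subjects using a variable matching ratio", with about twice as many matched controls as PrismRA patients. A control in a set with x controls gets weight Nc/(x·Nt), and the stated target is the average treatment effect on the treated (ATT). Missing outcomes are multiply imputed and estimates are pooled by Rubin's rule. For the primary endpoint, "Odds ratio and 95% CI will be estimated using weighted logistic regression". Change in CDAI uses weighted least squares.

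On p-values, SAP 5.3 says "P-values will be reported where appropriate to four decimal points" and sends the reader to Section 6 for methods. Section 6 gives odds ratios, mean differences and confidence intervals but no test statistic. The results shell, SAP Table 2.1, has no p-value column.

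**The concern.** A reader cannot tell which result decides superiority. The methods are not interchangeable. A chi-square or t-test in its ordinary form gives every control the same weight, so a 1:3 set contributes three times as much to the control rate as a 1:1 set. The SAP weights exist to undo that and recover the ATT.

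Set size depends on the propensity score, which is built from variables that plausibly predict response, such as baseline CDAI, RA duration and previous TNFi use. A link between set size and response is therefore plausible, though not documented.

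There is a second gap that needs no such link. The SAP expects roughly 45% and 50% of Week 24 outcomes to be missing and imputes them. Protocol 10.4 does not say how a chi-square would be combined over imputed data sets. On complete cases only, it would use the data of the SAP 6.3.2 sensitivity analysis and not those of the main analysis.

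The study is non-randomised and unblinded. Leaving more than one candidate primary p-value open allows a choice after the results are known.

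**Working it through.** **1. The plan's own figure.** Evaluable patients are 600 × 0.55 = 330 and 1,500 × 0.50 = 750. For 40% against 30%, two-sided 5%, exact enumeration of Fisher's test gives 88.4% power and the normal approximation to Pearson's test gives 89.1%. The stated 88% is reproduced. Fisher against Pearson hardly matters at these sizes; weighted against unweighted is what matters.

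**2. What the weights do.** With Nt = 600 and Nc = 1,200, w = 1,200/(600x) = 2/x, that is 2, 1 and 2/3 for x = 1, 2 and 3. Each matched set then carries total weight 2. Without weights, a set carries weight x.

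**3. Bias of the unweighted comparison under no effect.** Let p be the response rate in a set with x controls. The raw control rate is Σxp/Σx = mean(p) + cov(x, p)/mean(x). The PrismRA rate is mean(p), so the spurious difference is −cov(x, p)/mean(x). It is zero if x is constant or p is unrelated to x. It favours PrismRA if patients in 1:3 sets respond less, and goes against it if they respond more.

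**4. Assumed inputs.** The documents give neither the mix of set sizes nor the response gradient. Assume a mean response of 30%, the mixes below, and 5 or 10 points lower response in 1:3 than in 1:1 sets.

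- One third of sets at each ratio, 10 points (35%, 30%, 25%): raw control rate = (200×0.35 + 400×0.30 + 600×0.25)/1,200 = 28.3%; bias 1.7 points. The weighted rate is (400×0.35 + 400×0.30 + 400×0.25)/1,200 = 30%, so no bias.
- One third each, 5 points (32.5%, 30%, 27.5%): raw rate 350/1,200 = 29.2%; bias 0.8 points.
- Half 1:1 and half 1:3, 10 points (35%, 25%): raw rate = (300×0.35 + 900×0.25)/1,200 = 27.5%; bias 2.5 points.

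**5. From bias to type I error.** For the last case with 600 and 1,200 patients, the pooled rate is (180 + 330)/1,800 = 0.283. The standard error is √[0.283 × 0.717 × (1/600 + 1/1,200)] = 0.0225 and the shift is 0.025/0.0225 = 1.11. P(|Z + 1.11| > 1.96) is about 20%. With 330 and 600 patients the standard error is 0.0309 and the shift 0.81, giving about 13%.

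Simulation (40,000 replicates per scenario) agrees. Two-sided type I error of the unweighted test, with ranges covering both signs of the gradient:

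| Set mix | Gradient | 600 vs 1,200 | 330 vs 600 |
|---|---|---|---|
| Any | none | about 5% | about 5% |
| Thirds | 5 points | about 6.5% | 5.7% |
| Thirds | 10 points | 11% | 8.0-8.6% |
| Half 1:1, half 1:3 | 10 points | 19-20% | 12-13% |

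The weighted estimate was unbiased throughout, with type I error of 4.7-5.3%.

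**6. The other direction.** With thirds, response 10 points higher in 1:3 sets, a true 10-point benefit and 330 against 600 evaluable, the unweighted test had 72% power and the weighted one 84%.

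**The case against.** The strongest reply is that the documents already show which analysis governs. Protocol 10.3, 10.4 and 10.6.2 all refer to the SAP. SAP 5.3 points to Section 6, SAP 6.3 applies its methods to every endpoint, and the shells hold only model estimates with confidence intervals. A 95% interval implies a 5% test, and the SAP schedules no chi-square. On this view 10.4 is generic text written while weighting, matching and covariate adjustment were all still open.

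Much of this stands, and it lowers the severity. It does not close the point: weighted regression is a replacement for a chi-square and not a detail of it, and no sentence in the available text says that the SAP overrides 10.4 or that Fisher's test is for planning only.

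Three stronger readings are tempting and not supported.

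- A reader might infer that the chi-square is the only test named for superiority. Fisher's test is named for it in the power sections.
- A reader might infer that 10.4 tells the analyst to discard the weights. It places the comparison after propensity score modelling and is silent on weights; the unweighted result follows only from a literal reading.
- A reader might infer that the planned test is biased as such. The bias is conditional, can run against PrismRA, and vanishes with a constant ratio or no gradient. The 13% and 20% figures use the most uneven split that averages two controls per patient.

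**Conclusion.** The concern holds as an unreconciled primary test: Pearson, Fisher and weighted logistic regression are each attached to the same comparison, and the rule in Protocol 10.4 can give a wrong result if applied as written. It should be fixed, but it does not show that the reported result will be biased. Type I error ranges from the nominal 5% to about 6-11% under moderate assumptions, and to 13-20% under the uneven split with a 10-point gradient. The mix of set sizes and the gradient are assumptions, and the calculations ignore imputation, covariate adjustment and within-set correlation. The same weighting argument applies to the unpaired t-test on CDAI change, but its size was not calculated.

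**What to change.** - **Protocol 10.4:** replace the chi-square and unpaired t-test with the two-sided 5% test of the arm term in the SAP 6.3.1 weighted logistic model, pooled on the log-odds scale by Rubin's rules. For change in CDAI, use the arm term of the weighted least-squares model, pooled likewise.
- **SAP 5.3 and 6.3.1:** repeat that statement and name the variance estimator, which is missing now. It should be a robust variance that accounts for the weights and the matched sets.
- **SAP 6.3.1:** fix the covariates once. The section lists covariate adjustment as a step and later makes it optional. In a logistic model that choice changes the odds ratio being estimated.
- **Protocol 10.1 and SAP 5.1:** label Fisher's test a planning approximation only.

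The cost is a protocol paragraph and a few SAP sentences, settled before outcome data are analysed. No new data are needed.

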10.5 Missing Data Handling

Missing data will be handled with two approaches: (1) minimizing the chance of missing data in the study design and conduct stages, and (2) handling missing data with statistical methods in the analysis phase.

The following measures will be taken to reduce missing data in the analysis datasets.

PrismRA arm:

Missing data will be minimized through rigorous conduct of data collection as described in Section 8.9. See below for the handling of missing follow-up data.

External control arm:

At least one observed CDAI in the 3-month period prior to the index date (b/tsDMARD initiation) will be required to ensure patients are selected from practices where CDAI are recorded as a part of routine care.

The following statistical methods will be considered in handling missing data in the analyses.

- For outcome measures, the appropriate methods depend on the magnitude of missing data, and whether data are assumed to be missing at random. This will be evaluated prior to the final analysis and will be evaluated for the PrismRA arm and the external control arm separately. Considerations will be given to multiple imputation, estimating the CDAI outcome (whether MID was achieved at Week 24) based on previous outcome measures and treatment status, and complete case analyses. A sensitivity analysis will be conducted to assess the robustness of the analysis results. Details will be provided in the SAP.

10.6 Data Reporting

10.6.1 Interim Analyses and Reporting

A single interim analysis will be conducted at the time that 50% of PrismRA arm patients (the first 300 patients enrolled) have completed Visit 2 or have dropped out of the study. All data available in the PrismRA arm at the time of the interim analysis will be included, but effectiveness of PrismRA will not be evaluated to protect the integrity of the study. Instead, the interim analysis will be restricted to baseline characteristics and data completeness analyses.

10.6.2 Final Analyses and Reporting

A final study report will be generated after all data collection is complete. The final report will encompass all planned analyses, including a description of the complete study population and study results, as described in the SAP.

11 Limitations

11.1 Data Recency

An ideal observational external control arm is fully contemporaneous to the single arm trial with prospective real-world data collection specifically tailored to the corresponding PrismRA arm¹⁴. The approach is based on retrospective real-world data collection (secondary use of routinely collected data). Due to the need to have enough patients for the propensity score process, the external control arm may have a mixture of contemporaneous external control patients (observed during the PrismRA arm study period) and historical external control patients (observed before the PrismRA arm study period). In the SOC for RA, an increasing uptake of late-comer b/tsDMARDs has been reported for the 2001–2015 time period¹⁵. The market uptake trend may have been less dramatic in the more recent time period due to the paucity of new FDA approvals (last FDA approval: upadacitinib in 2019) and market saturation. However, the recent announcement (September 2021) by the FDA of a boxed warning for JAK inhibitors' regarding cardiovascular safety may have had an influence. In the current study, the historical external control patients will be limited to those who initiated their index b/tsDMARDs with the 1-3 year period prior to the trial enrollment (March 2022; minimum years that allows sufficient propensity score model patients). This approach should minimize the potential impact of a secular trend in the SOC (particularly the increasing uptake of non-TNFi b/tsDMARDs) while allowing for sufficient power.

11.2 RA Patient Identification

External control arm:

The identification of RA patients in the external control arm is based on the claims algorithm implemented in OM1's PremiOM RA dataset rather than the 2010 ACR/EULAR classification criteria. The algorithm uses RA diagnostic codes as well as DMARDs use. The combination of RA diagnostic code and DMARD use has a high positive predictive value (86.2%-88.9% against physician diagnosis gold standard)¹⁶ and is a well-accepted standard in the real-world data studies of RA. The OM1 claims algorithm likely has a higher positive predictive value as it incorporates further exclusion of patients with non-RA diagnoses for which DMARDs are indicated.

12 Data Handling and Record Keeping (Study Management)

PrismRA arm:

The design and conduct of the PrismRA arm will be governed by Scipher Medicine and its designees. OM1 will provide input to ensure the smooth execution of the subsequent analyses.

External control arm:

The design and execution of the observational external control arm and subsequent analyses will be performed by OM1, with the guidance, input, review, and approval of the Scipher Medicine

team. To ensure the quality and integrity of research, this study will be conducted under the Guidelines for Good Pharmacoepidemiology Practices (GPP) issued by the International Society for Pharmacoepidemiology (ISPE), the principles outlined in the Belmont Report (Ethical Principles and Guidelines for the Protection of Human Subjects of Research), and any applicable national guidelines.

